 - Other tasks measuring social perception
- 2: CASS (about 30 Minutes)
 - Interaction in study offices
 - 10 min with other children
 - Videotaped to analyze later
- 3: ERP
 - 45 minutes
 - Watch a social and non-social stimuli and press button in response to stimuli.
 - Wear a mesh hair net type device with tiny sponges.
 - Hair will get slightly damp, but that is the only possible discomfort.
- 4: Intervention
 - 10 consecutive sessions on for both the SENSE Theatre and TTT interventions.
- 5: Performance: Friday and Saturday evening (7:00pm) at end of the SENSE Theatre intervention.
- 6: Post and Follow-up Visits (Assessment, CASS, and ERP).

- Intervention will be free upon completion of all 3 parts (3 visits)
- **Explain randomization:** Your child may be randomly assigned to either the initial study group or an active control group for this study. If your child is assigned to the active control group, you will still complete the study procedures, but will participate in a separate type of intervention program.

VISIT SCHEDULING

General Notes:

- Add each component to Lab Calendar.
- Invite all site's lead investigator and other involved lab members to all scheduled calendar components.
- Give reminder call/email several days before event.

Assessment (2 hours)

- **Establish Days/Times** for when assessments can be scheduled.
- **Room Schedule:** Establish a separate calendar for room reservations. If there are any organizations or individuals that site space must be shared with, ensure those individuals are informed and there are no conflicts for space/scheduling.
- **Reserve Room:** Send email to [the research space coordinators](#) with room you are booking, Date, Times, and project for which the assessment room will be needed.
- **Parking:** Ensure all parking has been reserved for participants upon day and time of their visit.
- **Site Calendar:** Add Assessment to site Lab Calendar (Include Location, subject ID, and who is doing the assessment, in addition to any special notes : first time dx, needs ADOS, does not need ADOS, etc.)

ERP (45 minutes)

- Assessment and ERP are scheduled on the same day for pre-visits.
- Following the assessment, as long as the child meets criteria, give them a 15-30 minute break between assessment and ERP. Time to grab a snack, walk around, etc.

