Investigating Social Competence in Youth with Autism: A Multisite
RCT

Statistical Analysis Plan (SAP)

NCT03368001

Document Date: November 1, 2017

Document Source: Analytic Plan from MH114906

3.C.12. ANALYTIC PLAN: Aims and Hypotheses (Hyp)

Handling missing data, Full information maximum likelihood (FIML) estimation methods will be used.

Specific Aim 1: Show Efficacy of SENSE via Target Engagement of Memory for Faces

Hyp 1.1: Youth in the EXP group will demonstrate significantly faster growth in memory for faces (MFD and IMF) than youth in the ACC group. EXP youth will also have higher levels of memory for faces at follow-up.

Hyp 2.1: Youth in the EXP group will demonstrate significantly faster growth in social behavior (SRS and CASS) than youth in the ACC group. EXP youth will also have higher levels of prosocial behavior at follow-up.

Statistical Analysis: To address the above-mentioned hypothesis, we will use a 2-level multilevel growth model with treatment (EXP vs. ACC) predicting random intercepts and random linear slopes. The levels are (1) time of testing in months from study entry and (2) participant. Time will be centered at follow-up to enable interpreting the intercept as an end-point estimate. We will test EXP vs. ACC differences on means of the linear slope of time in order to test for differential change over time. We will also test EXP vs. ACC differences in follow-up-centered intercepts. A linear model is a reasonable model of social growth for such a short period (i.e., three months) with people who have a social impairment. The random intercept and slope accommodate dependency of time (pre, post, follow-up) within participant. Dependency of participants within cohort will be corrected for using design-robust standard errors (following procedures in Sterba¹²⁶). Site effects are not anticipated but will be examined by including 2 dummy covariates for site as predictors of intercepts and slopes; if not significant, these covariates will be removed. This model will be run in Mplus¹²⁷ general multilevel and structural equation modeling software capable of fitting both the univariate multilevel models for Specific Aim 1 and the multivariate multilevel models for Specific Aim 2, below.

Specific Aim 2: Linking Degree of Target Engagement and Mechanism-Based Functional Outcomes

Hyp 2.2. Growth in memory for faces (NEPSY, ERP) will mediate the effect of treatment on growth in social behavior (SRS, CASS).

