Power Using Attrition-adjusted Sample Size: Because missing data will be handled using FIML, the only dropouts will be those with no data (they were randomized but did not show up for any assessment). Past SENSE Theatre studies, including the previous RCT, had less than 10% post-Time 1 attrition. Virginia Tech, in unrelated, recent intervention RCTs had <17% attrition (teens) and 0% (adults); Stony Brook has had 0% attrition in recent RCTs of teens and adults. Thus, to plan conservatively, we will plan for a 90% retention rate. Power analyses were conducted using a proposed sample size that is adjusted for a 10% attrition rate, which is quite feasible. The probability of detecting a treatment effect and the effect size of between-group differences are understandably lower for dependent variables derived from far transfer procedures and for distal variables. The primary dependent variable (memory for faces) and the behavioral measure of social behavior (CASS variable) represent such outcomes. While the estimation of effect sizes from small pilot studies may be limited due to sampling variability¹³⁰, an established literature of theatre-based interventions does not exist. Using past meta-analyses of such outcomes and professional discussion about such effect sizes, clinically important outcomes for treatment-control differences in slopes are those exceeding Cohen's *d* of .25^{131,132}. The guidelines for effect sizes of indirect effects call indirect effects (i.e., product of the standardized coefficients for the x→m and m→y paths) greater than .10 'medium' effect sizes, and such effects are judged to be clinically important¹³³. Regarding Specific Aim 1, we anticipate a Cohen's *d* of at least .5 for the efficacy tests. Regarding Specific Aim 2, based on the past mediation analysis, we expect an indirect effect of at least .23. To demonstrate that our proposed sample size is more than adequate to detect even lower-than-expected effect sizes, we compute the minimally-acceptable effect size for 80% power with 216 participants. For the 2-level multilevel models used in investigating Specific Aim 1, with 216 participants, we will have 82% power for a Cohen's *d* as low as .2 with an ICC for within-participant dependence of .1. For Aim 2, involving mediation effects, we'll need a product of the x→m and m→y standardized coefficients of at least .056 with 216 participants using the confidence interval around the indirect effect to test significance¹³³. There will be plenty of power with the proposed sample size to detect the predicted effect sizes.

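### The Aim 1 power figure (82% at d = .2) allows only for dependence within a child and leaves out the within-cohort dependence that the SAP's own analysis corrects for

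*SAP*

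**What the plan says.** **Analysis.** In SAP 3.C.12, the Statistical Analysis paragraph for Hyp 1.1 and 2.1 sets out a growth model with two levels, occasion and participant. Cohort is not a level, but it is not ignored: "Dependency of participants within cohort will be corrected for using design-robust standard errors".

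**Power.** The paragraph on attrition-adjusted sample size sets its target with the words "we compute the minimally-acceptable effect size for 80% power with 216 participants". For Aim 1 it then reports "with 216 participants, we will have 82% power" for a d "as low as .2 with an ICC for within-participant dependence of .1". It gives no cohort or group ICC, group size, number of groups or design effect, for Aim 1 or Aim 2.

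**Benchmarks in the same paragraph.** Effects count as clinically important above d = .25 ("clinically important outcomes for treatment-control differences in slopes are those exceeding Cohen's" d of .25). The anticipated Aim 1 effect is a d of at least .5. The paragraph ends: "There will be plenty of power with the proposed sample size to detect the predicted effect sizes".

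**Delivery.** The Protocol's visit breakdown (Scheduling Participants) lists "10 consecutive sessions on for both the SENSE Theatre and TTT interventions". The sections on peers and counselors, training, and the intervention describe SENSE Theatre as a group production with a director, peers, a script and public performances. For TTT they mention sessions, a training director and peers, but do not describe a group structure.

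**The concern.** The analysis allows for a source of variance that the power calculation does not. Children who go through ten sessions together, with the same leader and peers, may gain or fail to gain together. That shared component does not average out across children in the same group, so 216 children carry less information about the treatment contrast than 216 independent children would.

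The stated figure has almost no room for this: 82% against a target of 80%. The d = .2 statement is the SAP's evidence that the sample is adequate even for effects smaller than expected. If the trial finds no difference, readers will judge that result against this stated sensitivity.

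**Working it through.** **Inputs from the SAP:** N = 216 (already reduced for 10% attrition); power 82% at d = .2; within-participant ICC .1; three occasions per child; target 80%; clinical-importance threshold d = .25; anticipated d at least .5.

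**Assumptions, because the documents do not say:** two-sided alpha .05 for Aim 1 (in line with the 95% interval used for Aim 2); 1:1 allocation; m = 5 to 12 children per arm-specific group; rho = .02 to .10. Here rho refers to the quantity being contrasted (a child's slope or follow-up level).

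**1. Reproducing 82%.** With 108 per arm, three observations per child and a within-child factor of 1 + (3-1)(.1) = 1.2, the effective number per arm is 108 × 3 / 1.2 = 270. The noncentrality is .2 × √(270/2) = 2.324, and power is Φ(2.324 - 1.960) = 64.2% two-sided (75.1% one-sided). Other two-sided versions at N = 216 gave 19% to 76.5%, apart from reading 216 as the number per arm. The 82% was therefore not reproduced. Alpha, sidedness, allocation, slope variance and the exact contrast are not stated for Aim 1, so this does not show that 82% is wrong. The steps below take the sponsor's figure as given.

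**2. Noncentrality implied by 82%.** z(.975) + z(.82) = 1.960 + 0.915 = 2.875.

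**3. Effect of grouping.** Let rho_c be the share of variance common to both arms of a cohort, and rho the share specific to one arm's group. The common part drops out of the contrast:

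design effect (DE) = 1 - rho_c + (m-1) rho

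With rho_c = 0 this is 1 + (m-1) rho. Power at d is Φ((2.875 × d/.2)/√DE - 1.960). The d that keeps 82% power is .2 × √DE.

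**4. Break-even with the 80% target.** DE = (2.875 / (1.960 + 0.842))² = 1.053. The corresponding rho is .053/(m-1): about .013 for m = 5, .009 for m = 7 and .005 for m = 12.

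**5. Scenarios (m and rho assumed).**

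| m | rho | DE | 216/DE | Power at d = .2 | d for 82% power | Power at d = .25 |
|---|---|---|---|---|---|---|
| 5 | .02 | 1.08 | 200 | 79.0% | .208 | 93% |
| 7 | .05 | 1.30 | 166 | 71.3% | .228 | 88% |
| 12 | .05 | 1.55 | 139 | 63.7% | .249 | 82% |
| 12 | .10 | 2.10 | 103 | 51.0% | .290 | 70% |

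**6. Predicted effect, same anchor.** At d = .5 the noncentrality is 2.875 × 2.5 = 7.19. At DE 2.10 it is 7.19/1.449 = 4.96, and power is Φ(3.00) = 99.9%.

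**7. Purely shared cohort effect.** With rho = 0 and rho_c = .01 to .10, DE is .99 to .90 and 82% becomes 82% to 86%.

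**The case against.** The strongest reply is that d = .2 is a stress test. It lies below the SAP's own threshold of .25 and far below the anticipated .5. The closing statement about ample power concerns the predicted effects, and on the sponsor's own anchor it survives (step 6). This stands. What weakens is the claim at d = .2 and, at the larger assumed design effects, at d = .25.

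Second, the size of the loss comes from assumed values of m and rho. This also stands: 79% to 51% is a scenario range, and other values widen it (80% at m = 6, rho = .01; 42% at m = 18, rho = .10). The break-even in step 4 depends less on the choice, because for groups of 5 to 12 an ICC of about .005 to .013 is enough to use up the margin.

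Third, group delivery of TTT is inferred rather than stated. If only the SENSE arm were clustered, the average DE over the same assumptions would be 1.04 to 1.55, and power at d = .2 would be 80.5% to 63.7%.

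Some stronger readings are tempting but not supported:

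- *That 82% is an upper bound, or that the corrected standard errors must be wider.* Only dependence specific to one arm's group lowers power. The documents do not say whether a cohort contains both arms; if it does, a shared cohort effect cancels and may slightly help (step 7).
- *That the trial is underpowered for d = .5.* A single follow-up comparison would give .5 × √(216/4) = 3.67, or 96% power, falling to 72% at DE 2.10. But that model gives only 31% at d = .2, so it is not the model behind the 82%.
- *That Aim 2 is undermined.* No Aim 2 figure has been recomputed, and the predicted indirect effect of .23 is about four times the stated minimum of .056.

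**Conclusion.** The point holds as a missing allowance. The SAP recognises within-cohort dependence in its analysis and omits it from the power statement, so the claim of 82% at d = .2 is unsupported as written. It is not shown to be an arithmetic error.

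The direction rests on some outcome dependence specific to an arm's group. The size rests on assumed m and rho, two-sided .05, and acceptance of the sponsor's 82% as the starting point. On those terms power at d = .2 is about 79% to 51%, and the d detectable with 82% power is about .21 to .29, which can exceed the SAP's threshold of .25. The finding concerns the power of the treatment contrast, not of either arm, and leaves the conclusion for the predicted d = .5 in place.

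**What to change.** In the SAP's power paragraph:

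1. State alpha, sidedness, allocation ratio, the contrast to which the power figure refers, the planned group size and number of groups per arm, and whether each cohort contains both arms.
2. Recompute the Aim 1 power and minimum detectable d with the design effect for group ICC .02, .05 and .10, or with an ICC from earlier SENSE data if one is available. Include d = .25 in the table.
3. Replace the d = .2 claim with the d that results.
4. Check whether the Aim 2 minimum of .056 changes under the same allowance.

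The number of groups matters in its own right. With 12 to 24 clusters (assumed) and a t reference on clusters minus 2 degrees of freedom, power at d = .2 is about 70% to 75% at DE 1.08 and 43% to 48% at DE 2.10.

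The cost is a few lines of text and a short table. Enrolment, conduct and the planned analysis do not change. The only downside is a less favourable stated figure.
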